7.4.4 Supplementary analysis

The same MMRM analysis method as described in [Section 7.4.1](#) will be applied on the mITT set (OC) to compare the change from baseline in HbA1c after 24 weeks of treatment between pooled Empagliflozin doses (10 mg q.d. and 25 mg q.d.) and placebo. The model includes treatment (Empagliflozin, placebo), background therapy (insulin only, insulin with OADs), and visit as fixed classification effects, baseline HbA1c and baseline eGFR as the linear covariates, treatment by visit interaction, and baseline HbA1c by visit interaction.

7.5 SECONDARY ENDPOINTS

7.5.1 Key secondary endpoints

This section is not applicable as no key secondary endpoints have been specified in the CTP.

7.5.2 Other secondary endpoints

The secondary endpoints for this study are described in [CTP Section 2.1.3](#).

7.5.2.1 Responder analysis

The HbA1c responder analyses will be performed on mITT (NCF) by determining the percentage of patients that fulfil responder criteria (for the definition of treat to target and relative efficacy response, see [Section 5.2.2](#)) by treatment. Non-completers considered failures (NCF) imputation-technique will be used to impute the missing data for this analysis strategy.

Each analysis will consist of a tabulation by treatment of the percentage of patients meeting the response criteria along with 95% exact confidence intervals for the percentage. Additionally, a logistic regression model with treatment, background therapy, baseline eGFR and continuous HbA1c will be fitted on the binary response variable to calculate the estimate of the odds ratio of each dose to placebo. Estimate of odds ratios and 95% confidence intervals (Wald) will be presented along with the p-values for each comparison.

7.5.2.2 Change from baseline in body weight, SBP, DBP and FPG

The MMRM models constructed for the primary endpoint will also be conducted for continuous secondary endpoints of change from baseline in body weight, SBP, DBP and FPG at week 24. Analyses will be performed on the mITT set (OC). The model will include the baseline value of the corresponding endpoint and its interaction with visit as covariates.

Proprietary confidential information © 2021 Boehringer Ingelheim International GmbH or one or more of its affiliated companies

7.5.2.3 Change from baseline in 2-hour PPG

A valid 2-hour PPG sample has to be taken between 1:50 and 2:10 h after the start of the meal in the MTT. To be eligible for use as baseline, the 2-hour PPG sample has to be taken prior to the intake of the first dose of the randomised study medication.

[figure not shown]
For continuous secondary endpoint of change from baseline in 2-hour PPG at week 24, ANCOVA will be performed based on the mITT (OC) set. The respective model will include treatment and background therapy as classification effects, baseline HbA1c, baseline PPG and baseline eGFR as the linear covariates.

7.5.2.4 Occurrence of hypoglycemic events and adjudicated DKA events

[figure not shown]
Number of patients with confirmed hypoglycemic events and adjudicated DKA events will be tabulated in frequency tables by treatment groups. Logistic regression will be performed to compare the occurrence of confirmed hypoglycemic events and adjudicated DKA events between empagliflorin groups (10 mg and 25 mg, respectively) and placebo. Odds ratios and their respective 95% confidence intervals and p-values will be obtained. Baseline HbA1c value and treatment will be included in the model. Time to the onset of the first event will be analysed by Kaplan-Meier estimates.

[figure not shown]
Summaries of hypoglycemic events will include total number of hypoglycemic events, descriptive hypoglycemic event rate, number of episodes per patient, severity and intensity of the worst episode, action taken, minimum glucose level of worst episode, and time to onset of first episode. Hypoglycemic events will also be summarised by background medication, type of insulin, age group and use of rescue medication.

Different tables will be shown for (i) patients with investigator defined asymptomatic or symptomatic hypoglycemia reported as AE or non-AE, and (ii) patients with confirmed hypoglycemic adverse events, i.e. hypoglycemic adverse events that had a plasma glucose concentration ≤ 70 mg/dL or required assistance.

Proprietary confidential information © 2021 Boehringer Ingelheim International GmbH or one or more of its affiliated companies

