### **3.3.3 Exclusion criteria**

1. Diagnosis of Type 1 diabetes;
2. Patients receiving MDI insulin or insulin pump treatment;
3. eGFR  $<45$  ml/min/1.73m^2 calculated based on MDRD formula;
4. Uncontrolled hyperglycemia [glucose level  $>13.9$  mmol/l after an overnight fast during placebo run-in];
5. Severe hypoglycemia episode (event requiring the assistance of another person to actively administer carbohydrate, glucagon or other resuscitative actions) within 6 months prior to Visit 1;
6. History of diabetic ketoacidosis or hyperosmolar non-ketotic coma.
7. Myocardial infarction, stroke or transient ischaemic attack within 3 months prior to Visit 1;
8. Bariatric surgery;

 A woman is considered of childbearing potential (WOCBP), i.e. fertile, following menarche and until becoming post-menopausal unless permanently sterile.

Permanent sterilisation methods include hysterectomy, bilateral salpingectomy and bilateral oophorectomy.

Tubal ligation is NOT a method of permanent sterilisation.

A postmenopausal state is defined as no menses for 12 months without an alternative medical cause.

Proprietary confidential information © 2021 Boehringer Ingelheim International GmbH or one or more of its affiliated companies

9. SGLT-2 inhibitors intake within 12 weeks prior to Visit 1;
10. Treatment with anti-obesity drugs within 12 weeks prior to Visit 1;
11. Treatment with GLP-1 receptor agonists within 12 weeks prior to Visit 1;
12. Treatment with SU if the patient is on premixed insulin within 12 weeks prior to Visit 1;
13. Impaired hepatic function (serum alanine aminotransferase, aspartate aminotransferase, or alkaline phosphatase >3 times the upper limit of normal) at V1;
14. Contraindication to background anti-diabetes medication according to the local label;
15. Disorders causing hemolysis or unstable red blood cells;
16. Treatment with systemic steroids at the time of consent;
17. Change in dosage of thyroid hormones within 6 weeks prior to Visit 1;
18. Alcohol or drug abuse within 12 weeks prior to Visit 1;
19. History of unstable or rapidly progressing renal disease;
20. Conditions of congenital renal glucosuria;
21. Known allergy or hypersensitivity to empagliflozin or other SGLT-2 inhibitors;
22. Major surgery (major according to the investigator's assessment) performed within 12 weeks prior to randomisation or planned within 28 weeks after screening, e.g. hip replacement;

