### **7.4 RANDOMISATION**

The trial will be performed as a double-blind design with respect to placebo and the two active dose groups of Empagliflozin (10 mg q.d. and 25 mg q.d.). The randomization will be stratified by the following factors:

- $\text{HbA}_{1c}$  value at screening visit (Visit 1) ( $<8.5\%$ ,  $\geq 8.5\%$ )
- Background antidiabetic therapy (insulin alone, insulin + OAD)

Block randomization will be used to randomize patients in a ratio of 1:1:1 to placebo or Empagliflozin 10 mg or Empagliflozin 25 mg.

BI will arrange for the randomisation and the packaging and labelling of trial medication. The randomisation list will be generated using a validated system, which involves a pseudo-random number generator so that the resulting treatment will be both reproducible and non-predictable. The block size will be documented in the Clinical Trial Report. Access to the codes will be controlled and documented.

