7.4.1 Primary analysis of the primary endpoint

The primary analysis is a restricted maximum likelihood (REML)based mixed model repeated measures (MMRM) approach comparing the change from baseline in HbA1c after 24 weeks of treatment. The analysis will be performed on the mITT set (OC) with treatment assignment as randomized and include on-treatment HbA1C only. If a patient misses a visit,

Proprietary confidential information © 2021 Boehringer Ingelheim International GmbH or one or more of its affiliated companies

the missing data will not be imputed. The mixed effect model will handle missing data based on a likelihood method under the “missing at random” assumption.

The statistical model will be:

Change in HbA1c (%) from baseline to the end of 24 weeks

[figure not shown]
= overall mean + treatment + background therapy + baseline HbA1c +
baseline eGFR + visit + treatment-by-visit interaction + baseline HbA1c-by-
visit interaction + random error.

The analysis will include treatment (Empagliflozin 10 mg, Empagliflozin 25 mg, placebo), background therapy (insulin only, insulin with OADs), and visit as fixed classification effects, baseline HbA1c and baseline eGFR as the linear covariates, treatment by visit interaction, and baseline HbA1c by visit interaction.

[figure not shown]
For each patient, the error terms from all the visits represent the within-patient variability and are assumed to follow a multivariate normal distribution with an unstructured covariance matrix. The random error is assumed to be normally distributed with mean 0 and unknown variance σ_j^2 . If an unstructured (co)variance structure fails to converge, the following structures will be tested in order: compound symmetry, variance components and Toeplitz. The (co)variance structure converging to the best fit, as determined by Akaike's information criterion, will be used.

The Kenward-Roger approximation will be used to estimate the denominator degrees of freedom and adjust standard errors.

A hierarchical testing sequence will be used as defined in the protocol. Superiority will be tested using the p-value of the treatment effect (least-squares means) and a two-sided 95% confidence interval for the treatment difference.

Proprietary confidential information © 2021 Boehringer Ingelheim International GmbH or one or more of its affiliated companies

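### The hypoglycaemia logistic model leaves out background therapy, a randomisation stratum used in every visible efficacy model; adding it is a free but modest improvement

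*SAP*

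**What the plan says.** Protocol 7.4 stratifies randomisation by two factors: HbA1c at Visit 1 (below 8.5% or not) and "Background antidiabetic therapy (insulin alone, insulin + OAD"). Within that scheme, "Block randomization will be used to randomize patients in a ratio of 1:1:1 to placebo" or either empagliflozin dose.

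The models visible in the SAP treat background therapy as follows:

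- Primary MMRM (7.4.1): included, as "background therapy (insulin only, insulin with OADs), and visit as fixed classification effects".
- Body weight, SBP, DBP and FPG (7.5.2.2): included by inheritance, since "The MMRM models constructed for the primary endpoint will also be conducted for continuous secondary endpoints".
- 2-hour PPG ANCOVA (7.5.2.3): included as a classification effect.
- HbA1c responder analysis (7.5.2.1): included; "a logistic regression model with treatment, background therapy, baseline eGFR and continuous HbA1c will be fitted on the binary response variable".
- Confirmed hypoglycaemia and adjudicated DKA (7.5.2.4): not included; "Baseline HbA1c value and treatment will be included in the model".

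So the hypoglycaemia model carries one stratification factor, as continuous baseline HbA1c, and drops the other. No reason is given. Protocol 7.2.3 specifies logistic regression with odds ratios, confidence intervals and p-values for this endpoint but names no covariates, so the choice was made in the SAP. SAP 7.5.2.4 also plans descriptive summaries of hypoglycaemia by background medication and by type of insulin.

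**The concern.** An analysis should normally reflect the factors used to stratify randomisation. Two things follow in logistic regression when a stratum that predicts the outcome is left out. First, stratified randomisation balances the factor across arms, but the model's standard error does not credit that balance, so the test rejects less often than its nominal level. Second, the odds ratio is non-collapsible: with a real treatment effect, the odds ratio averaged over strata is closer to 1 than the one within strata, even with perfect balance.

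Hypoglycaemia is a named secondary safety endpoint, and the risk table in Protocol 1.4.2 allows that it may rise when empagliflozin is added to insulin. In a safety comparison both effects act towards a quieter signal. The responder analysis uses the same method on a binary endpoint and does adjust, so the different treatment of hypoglycaemia looks unintended.

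**Working it through.** **Sample size.** Protocol 7.5 gives the only computable design figures, and these are for HbA1c: difference 0.62, SD 1.1, two-sided 0.05, censoring 8%, information content 0.4. The exact two-sample t-test needs 68 per arm (power 90.4%; Table 7.5:1 states 90.3%). Then 68 / (1 − 0.08 × 0.6) = 71.4, rounded up to 72. This reproduces the plan. There is no corresponding figure for hypoglycaemia, so 72 per arm is used below.

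**Assumptions.** The placebo risks in each stratum, the split between strata and the treatment odds ratio are not in the documents. The first set takes two equal strata, a within-stratum treatment odds ratio of 2.5, and placebo risks of 20%/30%, 20%/40% or 15%/50%. These imply stratum odds ratios of:

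- (0.30/0.70)/(0.20/0.80) = 1.7
- (0.40/0.60)/(0.20/0.80) = 2.7
- (0.50/0.50)/(0.15/0.85) = 5.7

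**Large-sample odds ratio without the stratum.** Multiply each stratum's placebo odds by 2.5, convert back to risks, average over strata, and form the odds ratio.

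- 20%/30%: treated risks 0.385 and 0.517, mean 0.451, against placebo mean 0.25. OR = (0.451/0.549)/(0.25/0.75) = 2.46.
- 20%/40%: 0.385 and 0.625, mean 0.505, against 0.30. OR = (0.505/0.495)/(0.30/0.70) = 2.38.
- 15%/50%: 0.306 and 0.714, mean 0.510, against 0.325. OR = (0.510/0.490)/(0.325/0.675) = 2.16.

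**Level of the test when treatment has no effect.** With the stratum balanced, the true variance uses the mean of p(1 − p) within strata, while the model without the stratum uses p̄(1 − p̄). The actual level is 2 × [1 − Φ(1.96/√ratio)].

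- 20%/30%: 0.185/0.1875 = 0.987, level 4.8%.
- 20%/40%: 0.200/0.210 = 0.952, level 4.5%.
- 15%/50%: 0.18875/0.219375 = 0.860, level 3.5%.

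**Simulation at 72 per arm** (3,000 trials per scenario; treatment plus a neutral continuous covariate, without and with the stratum term):

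| Placebo risk by stratum | Stratum OR | Median OR without / with | Power without / with |
|---|---|---|---|
| 20% / 30% | 1.7 | 2.50 / 2.56 | almost no difference |
| 20% / 40% | 2.7 | 2.40 / 2.54 | 72% / 73% |
| 15% / 50% | 5.7 | 2.22 / 2.60 | 65% / 71% |

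At a true odds ratio of 1 with risks of 15%/50%, rejection was 3.4% without the stratum and 5.1% with it, in line with the formula. A repeat with other random numbers gave power of 73%/75% and 64%/70% in the last two rows. The adjusted medians sit slightly above 2.5, which is small-sample overshoot, so the large-sample figures are the better measure of the shift.

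**Second set**, with a smaller effect and unequal strata (2,000 trials per scenario; within-stratum treatment OR 2.0, 70% on insulin plus OAD). Power without and with the stratum was:

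- 41.8% / 43.1% (overall placebo risk 20%, stratum OR 2)
- 45.7% / 48.5% (30%, stratum OR 3)
- 44.6% / 48.4% (30%, stratum OR 5)

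Rejection at a true odds ratio of 1 was about 4 to 5% either way. Over placebo risks of 10 to 40% and 50 to 85% on insulin plus OAD, the large-sample odds ratio without the stratum was 1.96–1.99 for a stratum OR of 2, 1.90–1.99 for 3 and 1.81–1.98 for 5, against a within-stratum value of 2.0.

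**Against the uncertainty.** The standard error of the log odds ratio is about 0.36 to 0.40. For an observed odds ratio of 2 the 95% interval is exp(0.693 ± 1.96 × 0.36) = 0.99 to 4.05, or exp(0.693 ± 1.96 × 0.40) = 0.91 to 4.38. The largest shift in the first set is ln(2.5/2.16) = 0.15 on the log scale, against a half-width of 1.96 × 0.36 = 0.71. Adjustment does not narrow the interval: with overall placebo risk 30% and a stratum OR of 3, the standard error goes from 0.357 to 0.367. Power rises because the estimate moves by more than the standard error does.

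**The case against.** A reader might infer that the planned odds ratio is biased and understates the hypoglycaemia risk of empagliflozin. The documents do not support that. Randomisation is stratified by background therapy, so there is no confounding. The two models estimate different quantities, one closer to marginal and one conditional on the stratum, and the first is not a distorted version of the second. Patient counts by arm will be tabulated in any case and depend on no model.

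A reader might also infer a strong stratum effect because sulphonylureas are allowed with basal insulin; the exclusion reads "Treatment with SU if the patient is on premixed insulin within 12 weeks prior to Visit 1". It is true that any sulphonylurea user falls in the insulin plus OAD stratum. But that stratum covers any OAD and does not identify sulphonylurea users, and the documents say neither how many there will be nor how risk differs by stratum. The planned summaries by background medication do not show that the sponsor expects a difference either, since age group and rescue use are listed alongside.

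The endpoint is outside the testing hierarchy in Protocol 7.1, and Protocol 7.2.5 calls safety analyses generally descriptive, with no testing planned. That stands, and it means no confirmatory conclusion depends on this model. It does not remove the point: Protocol 7.2.3 and SAP 7.5.2.4 still commit to odds ratios, intervals and p-values for hypoglycaemia, and once reported they should reflect the design.

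Finally, parts of the SAP are redacted, so the comparison with the efficacy models covers only those that can be read.

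**Conclusion.** The omission is real and unexplained. Its consequence is conditional and modest. Conservatism of the test requires that background therapy predict hypoglycaemia; the movement of the odds ratio towards 1 also requires a treatment effect. Neither can be checked from the documents, which give no event rates. At 72 per arm, under the assumed rates, the cost of omission is negligible for a weak stratum, about 1 to 3 points of power for a stratum odds ratio of 2 to 3, and about 4 to 6 points for 5 or more. Adjustment lost power in none of the scenarios examined. This is a free improvement in consistency with the stratified design, not the repair of an invalid analysis.

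**What to change.** In SAP 7.5.2.4, specify the logistic model for confirmed hypoglycaemia with treatment, background therapy (insulin only, insulin with OAD) and baseline HbA1c. Leave the DKA model unchanged: few events are likely, and a further term could make an ordinary logistic fit unstable.

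The cost is one model term in the SAP and the program, with no new data and no conflict with the protocol, which names no covariates here. Making the change before unblinding avoids a later choice between two models. If the sponsor prefers to keep the present model, one sentence giving the reason would suffice.

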#### **2.1.3 Secondary endpoint(s)**

[figure not shown]
Secondary efficacy endpoints are:

- Percentage of patients with HbA1c<7.0% after 24 weeks of treatment
- Change in body weight from Baseline to week 24
- Change in systolic blood pressure (SBP) from baseline to week 24
- Change in diastolic blood pressure (DBP) from baseline to week 24
- Change in Fasting Plasma Glucose (FPG) from baseline to week 24
- Change in 2-hour Post-prandial Glucose (PPG) from baseline to week 24

Secondary safety endpoints are:

- Occurrence of hypoglycemic events
- Occurrence of adjudicated diabetic ketoacidosis (DKA) events

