#### **5.2.7 Criteria for hypoglycemic events**

Every episode of plasma glucose  $\leq 70$  mg/dl ( $\leq 3.9$  mmol/l) should be documented in the eCRF with the respective time and date of occurrence. Such hypoglycemic events should be documented in the eCRF according to the following criteria:

- Asymptomatic hypoglycemia: event not accompanied by typical symptoms of hypoglycemia but with a measured plasma glucose concentration  $\leq 70$  mg/dl (3.9 mmol/l)
- Documented symptomatic hypoglycemia with glucose concentration  $\geq 54$  mg/dl and  $\leq 70$  mg/dl ( $\geq 3.0$  mmol/l and  $\leq 3.9$  mmol/l): event accompanied by typical symptoms of hypoglycemia
- Documented symptomatic hypoglycemia with glucose concentration  $< 54$  mg/dl ( $< 3.0$  mmol/l): event accompanied by typical symptoms of hypoglycemia
- Severe hypoglycemic episode: Event requiring the assistance of another person to actively administer carbohydrate, glucagon or other resuscitative actions.

Note for severe hypoglycemia: If another person hands the carbohydrate or glucagon to the patient without having to actively administer the substance because the patient is able to take the substance on his or her own, the hypoglycemic episode does not qualify as severe.

Any hypoglycemia with glucose values  $< 54$  mg/dl ( $< 3.0$  mmol/l) and all symptomatic or severe hypoglycemia events should be documented as an adverse event of hypoglycemia.

Further details on documentation of hypoglycemia are provided on the respective eCRF pages.

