#### 7.2.3 Secondary endpoint analyses

[figure not shown]
The percentage of patients with  $\text{HbA}_{1c} < 7.0\%$  after 24 weeks of treatment will be summarised in a frequency table by treatment groups and analysed using logistic regression. Odds ratios and their respective 95% confidence intervals and p-values will be obtained.

For continuous secondary endpoints of change from baseline in body weight, SBP, DBP and FPG at week 24, the similar MMRM approach based on on-treatment values for the primary analysis of the primary endpoint will be used. The model will include “baseline value for the corresponding endpoint” and its interaction with visit as additional covariates.

For continuous secondary endpoint of change from baseline in 2-hour PPG at week 24, an ANCOVA model will be applied since PPG is only measured at baseline and week 24. The ANCOVA model will include treatment and background therapy as classification effects, baseline PPG and baseline eGFR as the linear covariates.

Number of patients with hypoglycemic events and DKA events will be tabulated in frequency tables by treatment groups. Logistic regression will be performed to compare the occurrence of hypoglycemic events and DKA events between empagliflorin groups (10 mg and 25 mg, respectively) and placebo. Odds ratios and their respective 95% confidence intervals and p-values will be obtained.

More details of the analysis of secondary endpoints will be specified in TSAP.

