4 CHANGES IN THE PLANNED ANALYSIS OF THE STUDY

There are no changes in this TSAP compared to the statistical methods described in the CTP.

Proprietary confidential information © 2021 Boehringer Ingelheim International GmbH or one or more of its affiliated companies

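### The SAP fits the hypoglycaemia odds ratio to confirmed adverse events only, a narrower event set than the protocol's, without declaring a change

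*SAP*

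**What the plan says.** **Protocol.** Section 2.1.3 names the secondary safety endpoint as "Occurrence of hypoglycemic events", without qualification. Section 7.2.3 plans its analysis: "Logistic regression will be performed to compare the occurrence of hypoglycemic events and DKA events", each dose against placebo, with odds ratios, 95% intervals and p-values.

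Section 5.2.7 describes the events. Every episode at or below 70 mg/dL goes into the eCRF, and "Such hypoglycemic events should be documented in the eCRF according to the following criteria". The first category is "Asymptomatic hypoglycemia: event not accompanied by typical symptoms of hypoglycemia but with a measured plasma glucose concentration" at or below 70 mg/dL. The others are symptomatic episodes of 54 to 70 mg/dL, symptomatic episodes below 54 mg/dL, and severe episodes. A separate rule sets which events become adverse events: any value below 54 mg/dL, and "all symptomatic or severe hypoglycemia events should be documented as an adverse event of hypoglycemia".

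**SAP.** Section 7.5.2.4 applies the frequency table and the logistic regression to confirmed hypoglycaemic events. The last paragraph of that section describes two kinds of table. One covers asymptomatic or symptomatic hypoglycaemia, whether or not reported as an adverse event. The other covers confirmed cases, spelled out as "hypoglycemic adverse events that had a plasma glucose concentration" at or below 70 mg/dL, or requiring assistance. Section 5.2.2 takes the secondary endpoints as the protocol defines them, and Section 4 states: "There are no changes in this TSAP compared to the statistical methods described in the CTP".

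**The concern.** The protocol's event is set by a glucose threshold or by severity. The SAP's event adds adverse-event status as a condition. One protocol category, asymptomatic episodes of 54 to 70 mg/dL, meets the first definition but normally not the second.

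Hypoglycaemia is one of two declared secondary safety endpoints, and protocol Table 1.4.2: 1 says its risk may be increased when empagliflozin is combined with insulin. If the SAP is followed, the comparison with an odds ratio, interval and p-value that the protocol promises is not made on the protocol's events. A reader of the report who relies on SAP Section 4 would take the published odds ratio for the protocol endpoint.

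**Working it through.** **Step 1. Which events enter which analysis.**

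| Event | Protocol 5.2.7 event | Must be an adverse event under 5.2.7 | In the SAP regression | In the SAP descriptive table (AE or non-AE) |
|---|---|---|---|---|
| Severe (assistance required) | yes | yes | yes | not needed |
| Any, below 54 mg/dL | yes | yes | yes | yes |
| Symptomatic, 54 to 70 mg/dL | yes | yes | yes | yes |
| Asymptomatic, 54 to 70 mg/dL | yes | no | only if the investigator reports it as an adverse event | yes |

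Only the last row differs. Protocol 5.2.6.1.1 leaves a route into the regression for it, because findings on the home glucose log count as adverse events when the investigator judges them clinically relevant.

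**Step 2. Is the restriction already in the protocol?** The same SAP sentence speaks of adjudicated DKA, and that qualifier comes from protocol 2.1.3. The word confirmed has no counterpart for hypoglycaemia in protocol 2.1.3, 5.2.7 or 7.2.3. It first appears in the SAP.

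**Step 3. Size.** The documents state no hypoglycaemia rate, power or sample size, so there is no plan figure to reproduce. The one input they supply is the arm size in protocol 7.5: 68 / (1 − 0.08 × (1 − 0.4)) = 71.4, rounded up to 72. The rest is illustration on assumed rates.

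*Precision.* With 72 per arm and the same rate p in both arms, SE(log OR) = √{2 × [1/(72p) + 1/(72(1 − p))]}. Assume 20% to 40% of patients have any episode at or below 70 mg/dL, and that 30% to 60% of those have only asymptomatic episodes of 54 to 70 mg/dL.

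- Middle case, 30% and half: p goes from 0.30 (21.6 patients per arm) to 0.15 (10.8 per arm). The SE goes from √{2 × (0.0463 + 0.0198)} = 0.36 to √{2 × (0.0926 + 0.0163)} = 0.47.
- Smallest change, 40% and 30%: p goes from 0.40 to 0.28. The SE goes from 0.340 to 0.371, a ratio of 1.09.
- Largest change, 20% and 60%: p goes from 0.20 to 0.08. The SE goes from 0.417 to 0.614, a ratio of 1.47.

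*Odds ratio.* Assume 40% on placebo and 55% on active have any event.

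- All events: OR = (0.55/0.45)/(0.40/0.60) = 1.83.
- 30% of affected patients in each arm dropped: (0.385/0.615)/(0.28/0.72) = 1.61.
- 50% dropped: (0.275/0.725)/(0.20/0.80) = 1.52.

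Power for a two-sided 5% comparison of two proportions, normal approximation with 72 per arm, goes from about 44% to 27% and 18%. The risk ratio does not move (0.55/0.40 = 0.385/0.28 = 0.275/0.20 = 1.375), because the same share is dropped from each arm. In this example, then, the odds ratio changes because the event is rarer, not because a difference between arms has been hidden.

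**The case against.** Four points have force.

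1. **The link between the phrases is inferred.** The regression sentence speaks of confirmed events; the definition is attached to confirmed adverse events, in a sentence about tables. If confirmed in the regression meant only a glucose value at or below 70 mg/dL or assistance, nothing would be dropped. This stands as a caution. But the SAP gives no other definition, and if another was meant, the regression outcome is undefined and still needs correcting.

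2. **The protocol leaves detail to the SAP.** Section 2.1.3 does not define the event or cite 5.2.7, 5.2.7 is written as a documentation rule, and 7.2.3 defers further detail to the SAP. That covers additions such as the baseline HbA1c covariate. It does not stretch to replacing the set of events being compared.

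3. **A confirmed-event outcome is defensible.** During treatment, home testing is only recommended weekly, with extra tests when symptoms occur (protocol 5.2.5), so capture of asymptomatic episodes depends on how often a patient tests. This is a good reason to keep the confirmed-event regression, not to substitute it undeclared.

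4. **Consequences are limited.** The episodes stay in a descriptive table, and the endpoint is outside the testing hierarchy of protocol 7.1. Protocol 7.2.5 describes safety analyses as generally descriptive, without hypothesis testing. This stands.

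A reader might also infer that the whole endpoint now turns on investigators' willingness to file adverse events. It does not: 5.2.7 calls for an adverse event for every value below 54 mg/dL and every symptomatic or severe event. Discretion touches only the asymptomatic 54 to 70 mg/dL episodes.

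**Conclusion.** The mismatch is real and should be corrected. On the natural reading of SAP 7.5.2.4, asymptomatic episodes of 54 to 70 mg/dL that are not reported as adverse events leave both the main frequency table and the odds ratio, while SAP Sections 4 and 5.2.2 say the protocol is followed unchanged. This rests on two inferences: that 5.2.7 supplies the event definition for 2.1.3 and 7.2.3, and that the SAP's two uses of confirmed mean the same thing. Both are the ordinary reading; neither is stated outright.

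The size cannot be determined from the documents. The 9% to 47% larger standard error, and the shift in odds ratio from 1.83 to between 1.61 and 1.52, follow only from the assumed rates.

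Two stronger conclusions are not supported. A reader might infer that the SAP conceals a safety signal or biases the comparison, but the dropped episodes are still tabulated and nothing in the documents says they differ by arm. A reader might also infer that hypoglycaemia is the main added risk of the combination. The protocol says only that the risk may be increased, and reserves its language of particular concern in the risk table for DKA. The primary analysis and the hierarchical tests are unaffected.

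**What to change.** In SAP 7.5.2.4:

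- Add a frequency table and logistic regression for patients with at least one on-treatment event under protocol 5.2.7, adverse event or not, and label this as the protocol endpoint.
- State the on-treatment window for episodes not reported as adverse events. SAP 6.1 and Table 6.7:1 give windows for adverse events, laboratory values and pulse rate, but none for these. Using the 7-day adverse-event window would keep the two regressions comparable.
- Keep the confirmed-event regression alongside it, and say in one sentence what confirmed means, including whether adverse-event status is required.

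In SAP Section 4, list the confirmed-event analysis as an addition to the protocol, with its reason.

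The cost is one more regression and one extra table. The data should already be in the eCRF, since 5.2.7 requires every such episode to be entered. The drawback is that the added analysis includes mild asymptomatic episodes whose capture depends on home-testing frequency; a footnote to the table should say so.
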